2.2 Secondary Objectives

1. Determination of the prognostic ability of assays based on surface phenotype changes seen during homeostatic repopulation, including Ki67 expression, T_{REG} and B_{TRANS} cell surface phenotypes, and T_M to T_{REG}/B_{TRANS} balance, with regard to the anticipation of successful immunosuppressive drug withdrawal.
2. Assessment of the proposed therapies to prevent biopsy proven acute rejection at 1, 3 and 5 years post-transplant compared to the standard reported in the SRTR database for similar patients;
3. Assessment of the incidence of biopsy proven chronic allograft nephropathy at 1, 3 and 5 years post-transplant compared to that reported in the SRTR database for similar patients;
4. Assessment of the composite of occurrence of malignancies, and opportunistic infections by 1, 3 and 5 years compared to that reported in the SRTR database for similar patients;
5. Long term assessment of donor-specific immune responsiveness after prolonged therapy with belatacept (with or without sirolimus), and during and following drug

- withdrawal as determined by in vitro alloresponsiveness in CFSE mixed lymphocyte reactivity and ICCS;
6. Characterization of the repopulating immune system with regard to cell surface phenotype using MFC compared to prior experience with alemtuzumab alone or combined with other related regimens; and,
 7. Comparison of the function and survival of allografts transplanted using this protocol to historical controls transplanted using conventional immunosuppression to establish an initial assessment of this approach in a general transplant population.

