6.2 Maintenance Immunosuppressive Reduction

Beginning any time after year 1 (week 53), participants who are deemed eligible for sirolimus withdrawal as determined by clinical and flow cytometric parameters

(described below) may be withdrawn from sirolimus. Withdrawal will proceed at a maximum rate of 66% of the original dose for 4 weeks, 33% of the original dose for another 4 weeks, then discontinued. However, each reduction in dose will be predicated on stable flow cytometric profile.

Criteria for Sirolimus Withdrawal. Participants will be deemed eligible for withdrawal of sirolimus if they meet all of the following criteria:

1. No episodes of steroid resistant acute rejection since transplant, and no episodes of steroid sensitive rejection for 12 months.
2. Stable renal function, as defined by both of the following:
 - a. GFR, using calculated CrCl (Cockcroft-Gault) of > 40ml/min.
 - b. Creatinine, which in the 12 weeks preceding withdrawal has not increased more than 20% with respect to the lowest creatinine observed during the same period.
 - c. Absence of histologic evidence of acute or chronic rejection on pre-withdrawal renal biopsy according to the Banff criteria for acute, chronic and humoral rejection.
3. Absence of DSA reactivity, as measured by de novo anti-donor-HLA antibodies.
4. ALC at least 80% of the baseline ALC prior to alemtuzumab.
5. Ki67 expression on CD3+ T cells that is within 1 standard deviation of the normal expression in untreated controls. Ki67 is typically seen in <3% of lymphocytes in health controls and a value >5% exceeds the value accepted for purposes of this trial.

For determining eligibility, a renal biopsy will be obtained and creatinine clearance will be estimated. Requisite blood samples will be obtained within two weeks before starting sirolimus withdrawal. Results of laboratory assessments of immune status will be made available to, and reviewed by, the investigator. These data will be reviewed with the knowledge of previous results of immunosuppression withdrawal obtained in the current trial up to the time of review.

Maintenance Immunosuppressive Therapy

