9.2 Post-transplant Monitoring

Post-transplant Blood Monitoring. In general, functional monitoring will proceed in keeping with the standard of care for kidney transplantation at the Emory Transplant Center. Blood for testing of renal function (creatinine, BUN, hemoglobin/hematocrit) and electrolytes (including sodium, potassium, chloride, bicarbonate, magnesium, calcium and phosphorous) will be drawn daily until discharge and at least two times weekly for one month. Patients will be monitored weekly for at least 3 months or until the ALC exceeds 500 cells/mm³, whichever is longer. Thereafter, renal function will be assessed at least every two weeks until they reach their one-year evaluation. Lymphocyte repopulation and specific Ki67 and T_{REG} and B_{TRANS} phenotypes will be assessed monthly until 1 year after sirolimus elimination, and then every 3 months through 5 years by analysis of 7ml of heparinized blood by flow cytometry.

Biopsy Monitoring. A protocol biopsy will be performed following allograft reperfusion. Additional protocol biopsies will be performed at 6 months, and when the criteria for weaning to monotherapy belatacept are met (generally this will be during the second post transplant year) and again when the patient has been weaned to monotherapy belatacept for three months. An additional biopsy will be performed one year after weaning off sirolimus. It is assumed that histological acute allograft rejection is indicative of under-immunosuppression. Since histological rejection has been documented to occur in the absence of clinical renal dysfunction (so-called sub-clinical rejection) in up to 30% of persons with stable allograft function, it is reasonable to assume that some patients studied in this trial will have sub-clinical rejection, and thus be inappropriate for further immunosuppressive reduction. Protocol biopsies are thus clinically indicated to pre-empt inappropriate immunosuppressive weaning, as well as to detect other occult pathology

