9.3 Specific Tests and Evaluations

Donors

All live donors will provide written informed consent for participation in this trial. Donor characteristics (deceased or living, age, race, sex, medical history, laboratory tests, and ischemic time) will be documented. Live donors will be specifically informed of the experimental nature of their recipient's protocol. The living donor may decline to consent for the blood donation aspect of this protocol without affecting the recipient's ability to participate in this study. However if the donor declines to sign the informed consent for participation in all aspects of the protocol, the recipient may not be enrolled.

Recipient Evaluations Prior to Immunosuppressive Dosing

After informed consent is obtained, the following tests and evaluations are to be conducted within 72 hours prior to randomization/study treatment unless otherwise specified:

- Demographics
- Medical history
- Physical examination
- Vital signs
- Urinalysis

- Serum pregnancy test for females of childbearing potential
- CBC with differential
- Lymphocyte subsets, and baseline Ki67
- Peripheral blood transcription
- Donor specific MLR/ ICCS and antibody titers
- Blood chemistry: blood urea nitrogen (BUN), AST, ALT, total bilirubin, creatinine, sodium, potassium, calcium, bicarbonate, chloride, glucose
- HIV antibody, HBsAg, HCV Ab
- EBV and CMV IgG and IgM, and EBV and CMV PCR
- BK viremia and viruria
- Panel Reactive Antibody/ alloantibody assessment
- Donor characteristics including ischemic time

Evaluations During Treatment Period

See flowcharts in Section 8 for specific tests and the timing of test to be drawn during the study period. In addition, a general health related quality of life measure will be collected from all patients. We will utilize the SF-36 questionnaire. The instrument will be administered pre-transplant and at post-transplant visits in month 6, 12, 18, 24, then annually thereafter.

A neurologic assessment (exam and history) will be done every 3 months up to the year 2 annual visit. After year two, these assessments will be done every 6 months until the end of participation in the study.

The neurologic exam will include:

A review of any new neurological symptoms or changes, such as:

- Personality
- Memory
- Headaches
- Pain
- Seizures
- Impairment of consciousness
- Swallowing
- Vision, hearing, and language function
- Coordination
- Gait
- Weakness
- Sensory alterations
- Sphincter disturbances

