| 2 | CD2 | CD28 | CCR7 | CD27 | CD3 | CD8 | CD4 | CD14\20 | CD45RA | Memory |
| 3 | CD11a | CD38 | CCR7 | HLADR | CD3 | CD8 | CD4 | CD14\20 | CD45RA | Activation |
| 4 | CD103 | CD31 | CCR7 | CCR5 | CD3 | CD8 | CD4 | CD14\20 | CD45RA | Tregs |
| 5 | CD39 | FOX P3 | CD127 | CD25 | CD3 | | CD4 | CD14\20 | CD45RA | Treg |
| 6 | IgD | IgM | CD19 | IgG | CD27 | CD21 | CD5 | | CD38 | B cells |
| 7 | Ki67 | BCL2 | CCR7 | | CD3 | CD8 | CD4 | CD14\20 | CD45RA | intracellular |
| 8 | Perforin | Gran B | CCR7 | | CD3 | CD8 | CD4 | CD14\20 | CD45RA | intracellular |

will be derived directly and absolute cell counts will be extrapolated using the simultaneously drawn complete blood counts with differential accessed through merger of the Laboratory Information Management Software (LIMS) file with data from the Clinical Data Warehouse (see Resources). Assessments of baseline and subsequent values will be based on percentage data rather than absolute cell count, hypothesizing that ratios are more relevant after 1 year when the absolute cell count has normalized. This data stream is an established SOP and links all samples to clinical data through a HIPAA-compliant data merger. All flow panels are in daily use in support of this trial and the CTOT and CTOTC trials.

T cell assays assessing the peripheral T cell repertoire with regards to alloimmunity and protective immunity. Recognizing that diminished alloreactivity is relevant only if it is

specific for the allograft and does not come at the expense of protective immunity, we have and will continue to follow our patients for their capacity to protect themselves from opportunistic infection. In addition to clinical parameters (rejection, viremia), we will continue to evaluate alloreactive potential against donor and third party alloantigens, and viral specific T cell reactivity against CMV and EBV *in vitro* at time points indicated in the experimental plan above. This is vital to gain insight into the antigen specificity of any treatment effect. As discussed in the Preliminary Studies section, we are beginning to see elimination of donor allo-responsiveness but maintenance of non-donor responsiveness and CMV responsiveness. Quantitative *in vitro* measures of this repertoire migration are vital to understanding the durability of any observed clinical phenotype that emerges.

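### Appendix B assesses immune-subset values as percentages throughout, but its reason covers only the period after one year; first-year results for objective 6 should show absolute counts alongside.

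*Combined protocol and SAP*

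**What the plan says.** Appendix B sets the scale for the flow cytometry results: "Assessments of baseline and subsequent values will be based on percentage data rather than absolute cell count". The reason follows in the same sentence: "hypothesizing that ratios are more relevant after 1 year when the absolute cell count has normalized". The same paragraph makes the other scale available, since "absolute cell counts will be extrapolated using the simultaneously drawn complete blood counts with differential".

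Secondary objective 6 (section 2.2) is "Characterization of the repopulating immune system with regard to cell surface phenotype using MFC compared to prior experience with alemtuzumab alone" or combined with related regimens.

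The baseline precedes depletion: section 9.3 lists "Lymphocyte subsets, and baseline Ki67" among the tests done before any immunosuppressive dosing. Year 1 is sampled as well. Section 9.2 has the phenotypes assessed monthly, and the section 8.1 tables show lymphocyte subsets at enrollment, day 28 and month 6.

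On lymphocyte recovery, section 9.2 continues weekly monitoring for at least three months or "until the ALC exceeds 500" cells/mm³, whichever takes longer. Section 6.2 makes "ALC at least 80% of the baseline ALC prior to alemtuzumab" one of the criteria for starting sirolimus withdrawal after year 1. Section 4.2 describes secondary outcomes with summary statistics and gives no rule on the scale for subset data.

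**The concern.** The rule and its reason cover different periods. The rule applies to the baseline and every later value; the reason applies only after one year. The gap between them is the repopulation phase that objective 6 sets out to describe. Nor is normal ALC at one year assured for each patient, because section 6.2 makes recovery to 80% of baseline something still to be tested.

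After depletion, a subset's share of lymphocytes can rise simply because other subsets were depleted more. The protocol expects unequal depletion: Appendix B hypothesizes that memory T cells selectively resist alemtuzumab. On percentages alone, an early rise in regulatory T cells or transitional B cells over the pre-transplant value could be read as expansion, and so as a sign of immune regulation, when there are fewer of those cells in the blood. A comparison with earlier alemtuzumab cohorts could mislead in the same way if ALC recovered at a different pace in those cohorts.

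**Working it through.** The plan gives no figure to reproduce here. The check is an identity.

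**Inputs from the protocol.** ALC threshold for weekly monitoring: 500 cells/mm³ (section 9.2). ALC recovery for weaning: 80% of baseline (section 6.2).

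**Assumed inputs.** The protocol gives no baseline ALC, so I use 1000 to 2500 cells/mm³. The subset share of 5% rising to 10% is illustrative.

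**Formula.** For a subset reported as a percentage of lymphocytes, absolute count = percentage × ALC. Let r = ALC now / ALC at baseline, and f = percentage now / percentage at baseline. Then count now / count at baseline = f × r. The percentage rises if f > 1, and the count falls if f × r < 1. Both happen together when 1 < f < 1/r.

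**If ALC is at 500 cells/mm³:**

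| Baseline ALC (assumed) | r | 1/r | Count when the share goes from 5% to 10% | Change in count |
|---|---|---|---|---|
| 1000 | 500/1000 = 0.50 | 2.0 | 50 to 50 | 0% |
| 1500 | 500/1500 = 0.33 | 3.0 | 75 to 50 | −33% |
| 2000 | 500/2000 = 0.25 | 4.0 | 100 to 50 | −50% |
| 2500 | 500/2500 = 0.20 | 5.0 | 125 to 50 | −60% |

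The same doubling in percentage therefore goes with anything from no change to a 60% fall in cells, depending on the baseline.

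**At the weaning threshold.** r = 0.80, so 1/r = 1/0.80 = 1.25. For example, with ALC falling from 1500 to 1200 and the share rising from 5% to 6%, the count goes from 0.05 × 1500 = 75 to 0.06 × 1200 = 72, a fall of 4%. The window is narrow by then but not closed.

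**Where the formula does not apply.**
- A ratio of two subsets from the same gate is unaffected: (percentage A × ALC) / (percentage B × ALC) = percentage A / percentage B.
- Ki67 for weaning is read on CD3+ T cells (section 6.2). The relevant r there is CD3+ count over its baseline, not total ALC.
- Appendix B takes regulatory T cells and transitional B cells from the lymphocyte gate but does not state the reporting denominator. If it is a narrower parent population, r must be computed for that population.

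**The case against.** The case for leaving the plan alone has real substance.

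- **The 500 figure.** A reader might infer from section 9.2 that the plan expects ALC near 500 for weeks to months. It does not say so. The three-month minimum applies whatever the ALC, and 500 is a threshold for relaxing monitoring. The protocol text available gives no expected ALC course, so the table above is conditional.
- **Percentages only.** A reader might infer that counts are not available. They are derived in the same paragraph, and section 3.1 has ALC assessed monthly. What is restricted to percentages is the assessment.
- **The comparator.** Objective 6 names earlier alemtuzumab experience, and those patients were depleted too. A denominator artefact against them requires ALC recovery to differ between cohorts, which the documents do not show. The contrast with the pre-transplant value does not depend on that, and Appendix B does assess baseline and later values.
- **Ratios.** The balance of memory to regulatory cells in objective 1 is a ratio, and the Appendix B sentence is in part a defence of ratios. For subsets from one gate, that defence is sound.
- **Decisions.** Weaning begins after year 1 with its own ALC criterion, and section 3.1 follows surface phenotypes other than Ki67 only observationally.
- **Going further.** It is tempting to make absolute count the main scale until recovery and accept a change only when both scales agree. That would introduce a decision rule into a descriptive analysis and hide real enrichment. At r = 1/3, a 2.9-fold rise in percentage gives a count ratio of 2.9/3 = 0.97 and would go unreported, although enrichment of depletion-resistant memory cells is what the protocol hypothesizes.

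Reference 136 concerns compositional data, but I found no text that applies such a method; part of the first-cohort results in section 1.3.5 was not available to check.

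These points limit the size and reach of the problem. They do not close the gap between a rule for all time points and a reason for only some of them.

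**Conclusion.** The point holds as a limited reporting gap. In year 1 the percentage scale lacks the justification the protocol offers for it, and a single-subset percentage can rise while the number of cells falls. Under the assumed baselines of 1000 to 2500, the window for this extends to 2- to 5-fold if ALC is at 500 cells/mm³; it narrows to 1.25-fold at 80% recovery. These figures apply to percentages of all lymphocytes.

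What is affected is the interpretation of single-subset changes from baseline in objective 6, and of comparisons with other cohorts if their ALC recovery differs. The primary endpoint, weaning eligibility and same-gate ratios are not affected. A reader might go on to infer that any early rise in regulatory T cells or transitional B cells in this trial would be an artefact. The documents do not support that: the divergence is arithmetically possible, and nothing in them shows that it occurs.

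**What to change.** Amend the Appendix B sentence so that, for objective 6 and at least for every sample taken before ALC regains 80% of baseline, three quantities are reported side by side: the subset percentage (with its denominator stated), the absolute subset count already derived from the simultaneous blood count, and the ALC. Add that a percentage rise is not described as expansion of a subset unless the absolute count is shown with it. Keep percentages and ratios as the main scale after recovery, where the stated reason applies.

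The cost is extra table columns. No new sampling, assay or analysis method is needed, and no eligibility rule or endpoint changes.

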6.6 Treatment of Rejection

Biopsy proven acute rejection episodes will be treated based on the discretion of the transplant physician or surgeon. It will be permissible but not mandatory to continue protocol participation for patients who experience an early steroid sensitive rejection as described above. Presumed rejection episodes will be confirmed by biopsy as soon as possible after the initiation of symptoms. Biopsies will be performed at the Emory Transplant Clinic if at all possible. If patients are greater than a 24-hour trip from the center, the PI may elect to have the biopsy performed by a qualified transplant physician or surgeon. The Banff grade of rejection will be documented in the clinical case file and the date of the first episode of acute rejection will be the date the rejection is confirmed by biopsy. Management of rejections must be based on biopsy and clinical findings.

Patients with suspected rejection will undergo physical exam, laboratory evaluation, ultrasound examination of the kidney, and percutaneous renal biopsy accompanied by blood collection for peripheral phenotype analysis, transcriptional analysis and evaluation of donor specific alloreactivity. Biopsies will be evaluated by the attending transplant physician and reviewed with a pathologist skilled in the evaluation of renal transplant biopsy material. Biopsies will be evaluated using the Banff criteria for determination of allograft rejection.¹³⁰⁻¹³² Patients with biopsy proven rejection will be treated with methylprednisolone 500mg x 1-3 days. Failure to respond to methylprednisolone in no more than 3 days, or rapid worsening of graft function despite methylprednisolone therapy will prompt use of an approved antilymphocyte agent or other therapies deemed appropriate by the attending transplant physician or surgeon. After treatment of a steroid resistant rejection episode, patients will be discontinued from study treatment/immunosuppressive weaning and returned to a maintenance regimen established at the discretion of the attending transplant physician or surgeon in keeping with standard of care immunosuppression for renal transplantation. After treatment of a steroid sensitive rejection episode, patients may be restarted on the previous level of immunosuppression. The dosing and intensity of the regimen for maintenance

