8. STUDY OBSERVATIONS

8.1 Flow Charts/Time and Events Schedule

Month 1

| Tests / Evaluations | On Enrollment | | Day 7 Post-transplant (study day 8) | Day 14 (+/- 2 days) post-transplant | Day 21 (+/- 2 days) post-transplant | Day 28 (+/- 3 days) post-transplant |
|----------------------------------------------------------------------|----------------|--|-------------------------------------|-------------------------------------|-------------------------------------|-------------------------------------|
| Informed Consent | X | | | | | |
| Medical History | X | | | | | |
| Demographics | X | | | | | |
| Physical Examination | X | | X | X | X | X |
| Vital Signs | X | | X | X | X | X |
| Confirm Inclusion/ Exclusion criteria | X | | | | | |
| CBC with Differential | X | | X | X | X | X |
| Blood Chemistry/lipids | X | | X | X | X | X |
| Urinalysis | X | | X | X | X | X |
| Serum Pregnancy Test | X | | | | | |
| Sirolimus trough (study) | | | X | X | | |
| Donor-specific Antibody | X | | | | | X |
| Panel Reactive Antibody | X | | | | | X |
| Donor-specific and third party mixed lymphocyte responsiveness/ ICCS | X | | | | | |
| Lymphocyte Subsets-Ki67 | X ^a | | | | | X ^a |
| Peripheral blood transcription | X ^a | | | | | X ^a |
| Informed Consent | X | | | | | |
| HIV Ab | X | | | | | |
| HBsAg and HCV Ab | X | | | | | |
| CMV and EBV PCR | X | | | | | X |
| BK viremia/viruria PCR | X | | | | | X |
| Adverse Events | X | | X | X | X | X |
| QoL | X | | | | | |
| Immunogenicity | X ^a | | | | | |

^a These are specific study related assays for reporting purposes.

Months 2-6

| Tests/Evaluations | Every 2 Weeks | Monthly | Every 3 Months | At 6 Months | With Clinical Biopsies |
|-----------------------------------------------------------------------------------------------------|---------------|---------|----------------|----------------|------------------------|
| Physical Examination | | X | | | X |
| Vital Signs | | X | | | X |
| CBC with Differential | X | X | | | X |
| Blood Chemistry/lipids | X | X | | | X |
| Urinalysis | X | X | | | X |
| Sirolimus trough | x | | | | X |
| Lymphocyte Subsets Ki67 | | | | X ^a | X |
| Peripheral transcription | | | | X ^a | X |
| Donor-specific and third party mixed lymphocyte responsiveness/ other studies of hyporesponsiveness | | | | X | X |
| PRA | | | | X | X |
| Renal Biopsy | | | | X | X |
| Intra graft mRNA analysis | | | | X | X |
| | | | | X | |
| CMV and EBV PCR | | X | | | |

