In the first iteration of the trial, we proposed transcriptional analysis of blood and biopsy material and indeed have collected samples that we will evaluate as described in the initial study. These assays have been batched for analysis at the completion of the study as batch variation markedly alters interpretation of array-type transcriptional analysis. We will continue collection of samples as per our established protocol. Briefly, clinical samples will be procured and processed to RNA and PCR LDAs will be performed in the PI's lab. These arrays will be prospectively evaluated for their ability to segregate clinical outcomes in protocol patients and related to previously studied patients transplanted under standard of care immunosuppression. We have ample published experience with RT-PCR (TaqMan) in transplantation.¹²⁴⁻¹²⁶ Total RNA will be reverse transcribed to cDNA using TaqMan reverse transcription kit (Applied Biosystems) and amplified (50°C for 2min, 99°C for 10min, 40 cycles at 99°C for 15sec and 60°C for 1min) using 384-well LDAs (Applied Biosystems) or as individual target assays as necessary. Each amplification will be performed in quadruplicate and the mean values of quadruplicate assays will serve as the reported value. All samples will be compared to a pooled sample of cDNA from our established homogenous reference for normal kidney (pre-procurement live donor biopsy). Data will be analyzed and reported as described.¹²⁴⁻¹²⁶

We will construct a custom 384 well LDAs for these studies. These arrays will contain targets that we have shown to discriminate between subclinical and clinical acute rejection,¹²⁵ BK nephropathy,¹²⁶ and reperfusion injury.¹²⁴ These LDAs will allow for the validation of 98 genes in quadruplicate and will amply accommodate RT-PCR validation of 15 genes per condition and 20 known control genes for validation of results. Individual biopsy gene transcript data will be normalized by log transformation, and compared

between biopsy and blood samples with one-way analysis of variance (ANOVA). Post-hoc inter-group comparisons for different conditions will be made using a Bonferroni correction to appropriately account for multiple comparisons with significance defined as a two-tailed $p < 0.05$.

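### Appendix B compares biopsy and blood transcripts by one-way ANOVA with no patient term, although many of the samples share a patient and some share a visit; low priority, cheap to correct

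*Combined protocol and SAP*

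**What the plan says.** Appendix B, Transcriptional Studies, log-transforms the gene transcript data and compares them "between biopsy and blood samples with one-way analysis of variance (ANOVA"). It continues: "Post-hoc inter-group comparisons for different conditions will be made using a Bonferroni correction", with significance at two-tailed p<0.05. No paired test, blocking factor or patient effect is named. The same passage defers to other sources. It cites published papers ("Data will be analyzed and reported as described"), and for first-cohort material it says the investigators "indeed have collected samples that we will evaluate as described in the initial study".

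The sampling plan is elsewhere:

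- Section 8.1, Months 2-6, marks both "Intra graft mRNA analysis" and "Peripheral transcription" at 6 months and with clinical biopsies. The long-term tables list both assays in the yearly column, the biopsy under footnote b.
- Section 6.6 provides, for suspected rejection, "percutaneous renal biopsy accompanied by blood collection for peripheral phenotype analysis, transcriptional analysis and evaluation of donor specific alloreactivity".
- Section 9.2 has a biopsy after reperfusion and then: "Additional protocol biopsies will be performed at 6 months, and when the criteria for weaning to monotherapy belatacept are met". It adds two more after weaning. Footnote b in Section 8.1 instead leaves the biopsy on monotherapy to clinical indication, so the number of repeats per patient is not settled.

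**The concern.** One-way ANOVA takes its error term from all variation between samples, including stable differences between patients. When biopsy and blood come from one patient at one visit, those differences cancel in the contrast, but the test still charges for them. It is then too strict, and moderate differences can be missed.

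Repeat samples from one patient within a single condition cause the opposite fault. They carry less information than their number suggests, so the test is too lenient. Bonferroni does not help, because it addresses the number of comparisons and not dependence between samples.

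At stake is which transcripts are reported as differing in a mechanistic analysis that sets itself a p<0.05 rule.

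**Working it through.** **No figure to reproduce.** The documents give no effect size, SD, correlation, group size or power for this analysis. The figures below are illustrations.

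**Inputs.** From the documents: two-sided 0.05 (Appendix B); 20 patients in the new cohort (Section 3.1); about 40 in total (Synopsis), if first-cohort samples are included. Assumed: normal log expression, equal SDs, within-patient correlation ρ of 0.2, 0.3, 0.5 or 0.7, and shifts of 0.5, 0.8 or 1.5 SD.

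**Which samples match.** Same patient and visit: month 6, clinical biopsies, and the yearly column where a biopsy is done. Unmatched: blood at enrollment and Day 28 (no biopsy scheduled) and the reperfusion biopsy (no blood transcription scheduled that day).

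**Step 1: one biopsy-blood pair per patient, error rate.** With two groups, the ANOVA F is the square of the equal-variance t. The true variance of the mean difference is 2σ²(1−ρ)/n, but ANOVA uses 2σ²/n. In large samples the true error is therefore 2[1−Φ(1.96/√(1−ρ))]. At ρ = 0.5, 1.96/0.707 = 2.77, giving 0.56%. For the four correlations the formula gives 2.8%, 1.9%, 0.56% and 0.03%. Simulation with 20 pairs gives about 3%, 2%, 0.8% and 0.1%. The paired test stays at about 5%.

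**Step 2: power.** The paired test has noncentrality δ√n/√(2(1−ρ)). At δ = 0.8, n = 20, ρ = 0.5 this is 0.8 × 4.472/1 = 3.58 on 19 degrees of freedom, giving 92%. ANOVA power comes from simulation (60,000 runs per cell). Entries are ANOVA v paired, in percent.

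| ρ | 0.8 SD, 20 pairs | 0.8 SD, 40 pairs | 0.5 SD, 20 pairs | 0.5 SD, 40 pairs |
|---|---|---|---|---|
| 0.2 | 71 v 76 | 96 v 97 | 32 v 39 | 61 v 68 |
| 0.3 | 73 v 82 | 97 v 99 | 31 v 44 | 62 v 74 |
| 0.5 | 75 v 92 | 98.5 v 99.9 | 29 v 57 | 63 v 87 |
| 0.7 | 80 v 99 | 99.7 v 100 | 25 v 78 | 67 v 98 |

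At 1.5 SD both tests exceed 99% throughout. At ρ = 0 the ANOVA error is correct. Pairing then costs 2 to 3 points with 20 pairs (about 70 v 67% at 0.8 SD) and under 1 point with 40 (94.3 v 93.8%).

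**Step 3: two samples per patient pooled within a condition.** With k patients per condition, the true variance of a condition mean is σ²(1+ρ)/(2k), but the test assumes σ²/(2k). The error is 2[1−Φ(1.96/√(1+ρ))]. At ρ = 0.5, 1.96/1.225 = 1.60, giving 11%. Simulation of 10 v 10 patients gives 7%, 9%, 11% and 14% across the four correlations. At 0.05/3 = 1.67% (three comparisons) the error is 2.8% to 7.0%. At 0.05/6 = 0.83% (six) it is 1.6% to 4.6%.

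**Step 4: several visits pooled in a biopsy-blood contrast.** With 20 patients, three visits and a within-tissue correlation of 0.3 to 0.5, ANOVA error is 7% to 17%. A paired test on patient means holds about 5%. Pooling visits can therefore reverse the direction found in step 1.

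**The case against.** The strongest objection is that the sentence may not mean what it seems to. It opens with biopsy data and moves to post-hoc comparisons between conditions, which have no role after a two-group ANOVA. The stated aim of the arrays is to separate clinical outcomes. An ANOVA across conditions, using both sample types, fits about as well. This stands: the tested factor is unclear, and steps 1 and 2 apply only where tissue is that factor. On the other reading, the direction of error depends on whether a patient's samples fall in different conditions (too strict) or in the same one (too lenient), and the plan does not say.

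A second objection is that the cited papers or the initial study may already handle same-patient samples. They cannot be checked here. That possibility does not displace an explicit sentence naming one-way ANOVA, but it does allow a simpler remedy: write their method into the appendix.

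Third, every size above rests on assumed correlations. With 40 pairs and a 0.8 SD shift the loss is only 0 to 2 points. This also stands.

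A reader might infer more than the documents support:

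- That all biopsy and blood samples are paired. Enrollment and Day 28 blood and the reperfusion biopsy are not.
- That every comparison breaks independence. Appendix B also relates the arrays to previously studied standard-of-care patients. Those are different people, and independent groups are correct there.
- That the trial's main conclusions are at risk. The primary endpoint is reported descriptively with an exact interval (Section 4.2), and no objective in Section 2 uses the transcript results.

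**Conclusion.** The point holds in limited form. The named test assumes an independence that the sampling plan does not provide for same-visit biopsy-blood pairs or for repeat samples from one patient. Given positive within-patient correlation, the first case is too strict: at 20 pairs and 0.8 SD, power falls short by about 5 points at ρ = 0.2 and 19 at ρ = 0.7. The second case can be too lenient. With zero biopsy-blood correlation and one pair per patient there is no distortion, and large shifts are found either way. Which fault dominates cannot be told from the plan. This is an optional improvement to a mechanistic analysis, worth making because it is cheap.

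**What to change.** Replace the one-way ANOVA sentence in Appendix B with:

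> Log expression per gene will be analysed with a linear mixed model with fixed effects for sample type (biopsy or blood), visit and condition, as applicable to the comparison, and a random patient intercept, with Satterthwaite degrees of freedom. Where only one matched biopsy-blood pair per patient is compared, this is a paired t test. Comparisons with previously studied patients treat the two patient groups as independent. The Bonferroni correction across conditions is kept.

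The authors should also say for each comparison whether tissue or condition is the tested factor. If the cited papers already deal with same-patient samples, state that method instead.

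One limit: a single intercept assumes that a patient's samples are as alike across tissues as within one. If several visits enter one biopsy-blood comparison and that is doubtful, compare patient means per tissue by paired t test, as in step 4.

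The cost is SAP wording, a little more analysis work, and the power loss at zero correlation given under step 2. No new samples or visits are needed, because the assays are held for batch analysis at study completion.
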